### 2.7.3.2 eGFR by MDRD4

The eGFR by MDRD4 analyses will be based on FAS with multiple imputation used as the primary method for the handling of missing data. Renal function and change from Week 4 will be summarized by visit with descriptive statistics. A two-sided t-test will be performed to compare the two treatment groups at each visit. A plot of mean and 95% CI of eGFR (MDRD4) by visit will be provided. These will be repeated for on-treatment renal function analyses.

In addition, if different CNI effect is shown from the logistic regression, eGFR(MDRD4) and change in eGFR(MDRD4) from Week 4 by visit will be summarized for the subgroups of CNI (CsA and TAC).

The proportion of patients by eGFR(MDRD4) range (<30, 30-<45, 45-<60, ≥60 mL/min/1.73m^2) will be summarized by visit.

For eGFR(MDRD4) at Month 12 and Month 24, analysis of covariance (ANCOVA) will be performed with covariates/factors of treatment, CNI, region, interaction of treatment and CNI, interaction of treatment and region, donor type, HLA mismatch (≤3 vs >3), induction therapy, recipient gender, recipient age, donor age, DGF, and eGFR (MDRD4) at Month 1. In the model, recipient and donor age will be treated as continuous variables. The missing Month 12 or Month 24 values will be imputed using the primary multiple imputation method.

The evolution of renal function (eGFR by MDRD4) will be evaluated via a mixed effect model with intercept and study day as random effects and using covariates/factors treatment, study day, CNI, region, interaction of treatment and study day, interaction of treatment and CNI, interaction of treatment and region, donor type, HLA mismatch (≤3 vs >3), induction therapy, recipient gender, recipient age, donor age, DGF, and eGFR (MDRD4) at Month 1. In the model, study day, recipient and donor age, and eGFR (MDRD4) at Week 4 will be treated as continuous variables. Unstructured variance-covariance can be assumed, and the eGFR (MDRD4) data at Week 4 and onward will be used. The denominator degrees of freedom will be calculated using the Kenward-Roger method. No imputation will be applied for missing data. Based on the mixed effect model, the treatment groups will be compared, slope of renal function evolution for each treatment group will be assessed, and eGFR(MDRD4) value at Month 12/24 will be estimated.

See dummy SAS codes below.

```
proc mixed method=ml;
  class trt CNI region donor HLA induction gender_r DGF usubjid;
```

```
model eGFR= trt day CNI region trt* day trt*CNI trt*region donor HLA
induction gender_r age_d age_r DGF eGFR_1 / ddfm=kr;
random intercept day / patient=usubjid type=UN;
run;
```

## 2.8 Safety Evaluation

Safety variables to be assessed include discontinuation from study, discontinuation from treatment, AE/infection, SAE, notable events, laboratory tests, and vital signs. All safety analyses will be done on the safety set.

### 2.8.1 AEs Including Infections

Generally, infection data are analyzed together with AE data. In addition, infection data will be analyzed separately. Micro-organism will be additionally coded with NovORG dictionary. AEs and infections here refer to treatment-emergent events (on-treatment analysis by including data up to 7 days after the discontinuation of study drug). Treatment-emergent adverse events are defined as adverse events or infections that started after the first dose of randomized study medication or events present prior to the first dose of randomized study medication but that increased in severity. Selected variables will be analyzed using all available data including data assessed beyond study treatment discontinuation: SAEs and deaths.

In all summaries about incidence rates of AEs/Infections, if a patient had multiple occurrences of an AE, the patient will be counted only once in the corresponding AE category. If a patient had multiple adverse events within a system organ class, he or she will be counted only once for that class. If a patient had multiple severity ratings for an AE, he or she will only be counted under the maximum rating.

The following AEs/infections will be analyzed by system organ class and preferred term:

- Any events (AEs/infections)
- Frequent events ( $\geq 10\%$  in any treatment group)
- Events requiring study drug dose adjustment or temporary interruption
- Events leading to premature discontinuation of study drug
- Events suspected to be study drug related
- Events requiring study drug dose adjustment or temporary interruption or leading to premature discontinuation of study drug
- Events by maximum severity
- Serious events (SAEs/serious infections)
- Serious events suspected to be study drug related
- Death

Subgroup analyses will be done for AEs and SAEs including infections for the following subgroups:

- CNI (tacrolimus vs. cyclosporine)
- Region: US, EU, Asia, Australia, Latin America, and Middle East

Summaries by standard MedDRA query (SMQ) level (level 1 to 4, SMQ - narrow search) and preferred term will be produced for AEs and SAEs including infections, with relative risks and their 95% confidence intervals displayed.

All information pertaining to AEs noted during the study will be listed by patient, detailing AE (verbatim given by the investigator as well as the preferred term according to the MedDRA dictionary), body system, date starting and ending, causality, severity and drug-relatedness.

The MedDRA version used for reporting the study will be indicated as a footnote in the outputs.

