9.5.3 Safety variables

Safety variables to be assessed include discontinuation from study, discontinuation from treatment, AE/infection, SAE, notable events, laboratory tests, and vital signs. All safety analyses will be done on the safety set. Generally safety analyses will use treatment -emergent data (on-treatment analysis by including data up to 2 days after the discontinuation of study drug). Selected variables will be analyzed using all available data including data assessed beyond study treatment discontinuation: AEs/infections and deaths.

As subjects may not necessarily visit the clinics at the exact scheduled time, it may be misleading to lump all data with the same nominal visit number into the same visit in a by-visit analysis. Thus, all data are to be "re-aligned" by referencing their visit date to the date of initial dose. Visit-based time windows will be defined for data analysis.

The Baseline value is represented by the last observation during the Baseline period.

Amended Protocol Version v01 Clean

Assessment of premature study and study treatment discontinuation

Incidence rate of subjects who prematurely discontinue study medication or study will be summarized by frequency tables.

AEs/infections

Generally, infection data are analyzed together with AE data. In addition, infection data will be analyzed separately. Micro-organism will be additionally coded with NovORG dictionary.

The incidence of treatment-emergent AEs will be summarized by body system, severity and relationship to study drug. The type (viral, bacterial, fungal, and others) and micro-organism of infections will be tabulated. In addition, AEs/infections will be summarized per SMQ narrow search.

All information pertaining to AEs noted during the study will be listed by subject, detailing AE (verbatim given by the investigator as well as the preferred term according to the MedDRA dictionary), body system, date starting and ending, causality, severity and drug-relatedness.

Notable events

Notable events include death, non-fatal SAEs (including infections and rejections reported as SAE), AEs (including infections and rejections) leading to discontinuation from the study, and drop-outs due to notable events as reported on the Treatment/Study completion CRF): a) adverse event(s); b) abnormal laboratory result(s); c) abnormal test procedure result(s).

Vital signs

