### 2.1 Data Analysis General Information

The cut-off day is defined as the latest study day before and up to which data will be used in the analysis on an individual patient level. The cut-off date for 12-month analysis will be the day of Month 12 Visit (specifically, Date of Discontinuation/Study Phase Completion as recorded on the Month 12 Disposition eCRF) + 2 Weeks, but no later than Day 450 (upper limit of Month 12 analysis window). For the 24-month analysis, there will be no cut-off day. All data in the clinical database will be used for the analyses.

Data listings will include all data collected up to the cut-off date for the 12-month analysis, or all data recorded in the database for the 24-month analysis.

For summary tables and figures, the following rules will be applied unless otherwise indicated:

- Categorical data will be summarized by frequencies and percentages. Continuous data will be summarized by mean, median, standard deviation, minimum and maximum and the number of non-missing data points.
- All AE/Infection, notable events, CMV information, EBV information and other events of interest will be summarized based on all collected events with onset on or after the first day of study medication up to the cut-off date or seven days after last dose of study medication. For SAE/infection and death, all events will be summarized.
- All lab or vital sign tables will include data up to the cut-off date or two days after last dose of study medication (on-treatment analysis);

- Efficacy and renal function analyses will be primarily based on all available data including those after study medication discontinuation; as a sensitivity analysis they will include only data up to two days after last dose of study medication (on-treatment analysis). Patients will be censored for the time to event analyses if they do not have an event. For on-treatment analysis, the censoring day is two days after discontinuation of study medication or the last contact day, whichever is earlier; for analysis regardless of on-treatment or off-treatment, the censoring day is the last contact day.
- For post-baseline continuous values, for a given patient, if multiple numeric measurements for a given variable are reported within the same visit window (see the definition for visit windows in [Section 4.1](#)), the following rule will be applied:

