### 2.1.1.5 On-Treatment

An *on-treatment* observation will be any assessment obtained on and after Day 1 but no later than two days after the discontinuation of randomized study medication. However, for AE/Infection, notable events, CMV information, EBV information and other events of interest, events occurring up to seven days (inclusive) after discontinuation of study medication are considered “*on-treatment*”.

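### The SAP narrows the protocol's all-data rule from AEs/infections and deaths to SAEs and deaths, so non-serious AEs and the events-of-interest risk ratios have no between-arm summary beyond 7 days after last dose

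*SAP*

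**What the plan says.** **Protocol.** Sections 9.1 and 9.5.3 set a general on-treatment window of two days after stopping study drug and then make an exception: "Selected variables will be analyzed using all available data including data assessed beyond study treatment discontinuation: AEs/infections and deaths". Section 9.5.3 also plans an on-treatment table: "The incidence of treatment-emergent AEs will be summarized by body system, severity and relationship to study drug". Sections 3.1 and 5.5.9 keep patients who stop the regimen in the study to Month 24. Section 2.2 lists as secondary objectives, by treatment group, the incidence of CMV and BKV, new-onset diabetes, chronic kidney disease with proteinuria, major cardiovascular events and malignancies.

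**SAP.** Section 2.1 states "All AE/Infection, notable events, CMV information, EBV information and other events of interest will be summarized" from first dose "up to the cut-off date or seven days after last dose of study medication". The next sentence reads "For SAE/infection and death, all events will be summarized". Section 2.1.1.5 repeats the window: for the same classes of event, "events occurring up to seven days (inclusive) after discontinuation of study medication are considered" on-treatment. Section 2.8.1 says "AEs and infections here refer to treatment-emergent events (on-treatment analysis by including data up to 7 days after the discontinuation of study drug", and then gives the exception as "Selected variables will be analyzed using all available data including data assessed beyond study treatment discontinuation: SAEs and deaths". Sections 2.8.2 and 2.8.3 plan risk ratios with 95% CIs for malignancy, major cardiovascular events, new-onset diabetes, proteinuria, infections and polyomavirus infection, among others. The document history gives consistency across the programme as the reason for seven days. It does not mention dropping the all-data analysis of AEs and infections.

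**The concern.** The SAP sentence has the same form as the protocol sentence but a shorter list. Events named as secondary objectives are therefore compared between arms over a window that ends when each patient stops the regimen, although follow-up continues. SAP 2.1 bases efficacy and renal function primarily on all available data, including after discontinuation, so benefit and non-serious harm would be counted over different periods.

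A crude proportion over a truncated window depends on how long patients stay on the regimen. If one arm stops more, it has less time in which an event can count, and its risk ratio is pulled down without any difference in hazard. The window also has different end-points in the two arms. Under SAP 2.1.1.2 it runs from the last everolimus intake in the investigational arm, but from the earliest last dose of any regimen drug in the MPA arm. A patient who stops the CNI first is cut off in one arm and not in the other.

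**Working it through.** No figure in the plan is at stake, so there is none to reproduce. The first step compares the texts; the second is an illustration of scale.

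**Step 1: the rules side by side.**

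| | Protocol 9.1, 9.5.3 | SAP 2.1, 2.1.1.5, 2.8.1 |
|---|---|---|
| Default window | 2 days after stopping | 7 days for AEs, infections, CMV, EBV and events of interest; 2 days for laboratory and vital signs |
| All-data exception | AEs/infections, deaths | 2.8.1: SAEs, deaths. 2.1: serious events and deaths, with infections unclear |

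**Step 2: where an event after the window would appear.**

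- Malignancy: Protocol 7.1 makes every malignant neoplasm serious. It stays in the all-data SAE tables and in the SMQ-level relative risks that SAP 2.8.1 plans for SAEs. Its separate events-of-interest risk ratio is truncated.
- Serious cardiovascular events, infections and diabetes: the same.
- Non-serious cardiovascular and diabetes AEs: patient listings only.
- Non-serious CMV and BKV: listings only if the infection wording in SAP 2.1 means serious infections; summarised on all data if it means all infections. SAP 2.8.1 supports the first reading.
- Laboratory-based proteinuria and the glucose criterion for diabetes: not covered by the protocol's exception, so the SAP does not depart from it here.

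**Step 3: scale.** The documents give no discontinuation rates or stop times. Both are assumed below, with the same true constant event hazard in both arms, so the correct ratio is 1.00.

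*(a) All stops at Month 6, horizon 24 months, 7 days ignored.* The share of follow-up inside the window is 1 − d × 18/24, where d is the proportion stopping.
- d = 30%: 1 − 0.30 × 0.75 = 0.775
- d = 20%: 1 − 0.20 × 0.75 = 0.85
- Ratio: 0.775/0.85 = 0.91

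Over a 12-month horizon the shares are 1 − 0.30 × 6/12 = 0.85 and 1 − 0.20 × 6/12 = 0.90, and the ratio is 0.94.

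*(b) Constant stopping hazard over 720 days, 7-day window.* λ = −ln(1 − d)/720. The expected window is 7 + [1 − exp(−713λ)]/λ days.

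| d by Month 24 | Share of follow-up outside the window |
|---|---|
| 10% | 5.0% |
| 20% | 10.2% |
| 30% | 15.6% |
| 40% | 21.3% |
| 50% | 27.4% |

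With a true 24-month risk of 5%, the captured risks are 4.50% (d = 20%), 4.23% (30%) and 3.94% (40%). The ratios are 4.23/4.50 = 0.94 for 30% versus 20% and 3.94/4.50 = 0.88 for 40% versus 20%. For true risks from 3% to 20% these ratios stay at 0.94 and 0.88.

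*(c) Length of the window.* At d = 30%, a 7-day window leaves out 15.6% of follow-up and a 2-day window 15.8%. The change from two to seven days hardly matters; the missing all-data analysis does.

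**The case against.** The strongest reply is that on-treatment safety tables are a legitimate choice and that the protocol plans one itself. Its all-data sentence prescribes no particular table and does not name events of interest. SAP section 2 follows protocol section 9 unless otherwise indicated, so the departure is written down. All-data tables have weaknesses too. Off-regimen patients need attend only from Month 6 onward (protocol Table 6-1, footnotes), so ascertainment is thinner before then. SAP 4.2.1.2 expects everolimus patients to move to control-like treatment, which dilutes the contrast. All of this stands. It justifies keeping the 7-day tables; it does not justify omitting the analysis that the protocol promised beside them.

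Three stronger readings are tempting and are not supported:

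- A reader might infer that late malignancies or serious cardiovascular events drop out of the comparison. They do not: serious events remain on all data, with relative risks at SMQ level.
- A reader might infer that late non-serious events are lost. SAP 2.8.1 lists all AEs noted during the study; what is missing is a between-arm summary. For BKV and diabetes the cut itself is inferred, because SAP 2.1 does not name BKV and the diabetes definition in SAP 2.8.4.3 gives no end date.
- A reader might infer that the plan favours everolimus. The documents do not say which arm stops more, and the last-dose rule in SAP 2.1.1.2 can only lengthen the everolimus window relative to the rule used for MPA. The direction is unknown.

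**Conclusion.** The conflict between protocol 9.1/9.5.3 and SAP 2.8.1 is real and unexplained, and SAP 2.1 and 2.8.1 do not agree clearly with each other on infections. What is missing is an all-data between-arm summary of non-serious AEs and of the events-of-interest risk ratios. For non-serious CMV and BKV this holds only if the infection wording in SAP 2.1 means serious infections.

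The possible distortion is moderate: about 6% to 9% on the risk ratio for 30% versus 20% stopping, and about 12% for 40% versus 20% under a constant stopping hazard. These figures rest wholly on assumed rates and timing and on equal, constant event hazards. With equal stopping and equal windows the expected ratio stays at 1.00. The primary and key secondary analyses are not affected. The point should be corrected because named secondary objectives depend on it and the data are already collected.

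**What to change.** Keep the 7-day tables. Beside them, specify all-data tables to the Month 12 and Month 24 cut-offs, with the same risk ratios and CIs where SAP 2.8.2 and 2.8.3 plan them, for AEs/infections overall and for the AE-based secondary-objective events: CMV, BKV, new-onset diabetes, proteinuria reported as AEs, major cardiovascular events and malignancy. State in SAP 2.1 and 2.8.1, in the same words, whether all infections or only serious ones are on all data. For diabetes, say how antidiabetic drugs started after stopping the regimen are counted, since SAP 2.4.3 does not treat them as concomitant. Laboratory-based items stay as they are.

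The cost is a second set of tables on existing data, read with the thinner early visits and the dilution after stopping in mind. Trial conduct, sample size and alpha do not change.

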## Infections

The derivation of the infection type (viral, bacterial, fungal, and others) is based on the coded microorganism. Microorganisms are coded with NovORG (Novartis Organism Dictionary). The codes in NovORG are text strings of seven characters, L-*abcde*, where *a, b, c, d*, and *e* may be numbers or letters, e.g., L-1E601 (for *enterococcus faecalis*), L-24801 (for *staphylococcus aureus*) and L-43131 (for *candida albicans*). The 3rd character, *a*, will be used to determine infection type defined in [Table 2-3](#).

**Table 2-4 Novartis Organism Dictionary Categories for Infections**

NovORG Code	Infection Type
L-1bcde, L-2bcde	Bacterial
L-3bcde	Viral
L-4bcde	Fungal
L-xbcde, where x ≠ 1,2,3,4.	Other
Infections may not have been cultured or may have been recorded on the Adverse Events eCRF, for all such events the organism type is unknown	Unknown

In addition to summarizing infections together with AEs, the infections will be also tabulated by infection type (viral, bacterial, fungal, and others) and micro-organism of infections.

### 2.8.2 Safety Events of Interest

Safety events of interest, such as risks defined in the Safety Profiling Plan, Risk Management Plan or events of interest regarding signal detection or routine analysis are defined in the Program Case Retrieval Sheet (CRS) that is stored in CREDI at the path Cabinets/CREDI Projects/R/RAD001A/Integrated Medical Safety.

The following safety events of interest will be summarized with the number and percentage of patients experiencing the events, together with risk ratios (RRs) and 95% CIs. The version of the Case Retrieval Sheet used for the analyses will be described in a footnote. This includes MedDRA version and NMQ (Novartis MedDRA Queries) dictionary date.

- Anemia: Haematopoietic erythropenia (SMQ, broad search)

- Gastrointestinal ulcers: Gastrointestinal ulceration (SMQ, narrow search)  
This is a sub-SMQ under "Gastrointestinal perforation, ulceration, haemorrhage or obstruction (SMQ – narrow search)"
- Interstitial lung disease (CRS)
- Hyperlipidemia (CRS)
- Major cardiovascular events: Ischaemic heart disease and Cardiac failure (SMQ narrow search)
- Malignancy (CRS)
- NODM (See [Section 2.8.3.3](#))
- Peripheral edema (CRS)
- Proteinuria (associated chronic kidney disease) (CRS)
- Pleural effusion: MedDRA preferred term "Pleural effusion"
- Renal failure, excluding proteinuria (CRS)
- Stomatitis/mouth ulceration (CRS)
- Thrombocytopenia: Haematopoietic thrombocytopenia (SMQ, narrow search)
- Thrombotic and thromboembolic events: Embolic and thrombotic events (SMQ)
- Thrombotic microangiopathy (CRS)
- Wound healing events/disorders or complications: See [Section 4.4.1](#).

### 2.8.3 Program Specific Safety Risk Events

The following program specific safety risk events as defined in the Program CRS will be summarized with the number and percentage of patients experiencing the events, together with risk ratios (RRs) and 95% CIs.

- Angioedema
- Chronic allograft nephropathy
- Edema (including peripheral edema)
- Everolimus and calcineurin inhibitor (CNI) induced renal dysfunction
- Exposure in pregnancy/breast-feeding women
- Hyperlipidemia
- Impaired male fertility
- Infections
- Infections (Polyomavirus infection)
- Interstitial lung disease
- Leukopenia and pancytopenia
- Malignancy
- New onset diabetes mellitus (NODM)
- Proteinuria (AE based definition)
- Proteinuria (lab based definition)
- Renal graft thrombosis
- Stomatitis and Mouth ulceration
- Teratogenicity

- Thrombotic microangiopathies (TMA)
- Venous thrombosis
- Wound-healing complications

## 2.8.4 Other Safety Events

### 2.8.4.1 CMV

The incidence of CMV infection within each treatment group will be tabulated by donor versus recipient CMV serology pattern. Other CMV infection-related information including CMV syndrome, CMV disease with organ involvement will be tabulated by treatment group.

Additionally, CMV infection, syndrome and disease will be analyzed by donor/recipient CMV serology status pre-transplantation and CMV prophylaxis. Within each CMV serology status, the Cochran Mantel Haenszel test will be used to examine differences between the treatment arms adjusting for the presence/absence of CMV prophylaxis. CMV prophylaxis is defined as the use of antiviral drugs specified in [Table 2-4](#) within 14 days of transplantation that are taken consecutively for 30 days or more.

